12.2.2 Safety variables

Analysis of time from first dose of study medication to each of the following endpoints will be performed:

- The first PLATO major bleeding event
- Discontinuation of study medication due to any bleeding event

Treatment groups will be compared using the Cox proportional hazards model with a factor for treatment group. Kaplan-Meier estimates of the cumulative incidence of each event will be calculated and plotted and 95% CI for the hazard ratios presented. The safety assessment will also include analysis of total major bleeding events, fatal bleeding events, fatal or life threatening bleeding events, combined major and minor bleeding events across different categories as well as different categories of major and minor bleeding events separately. Exploration of potential risk factors for bleeding events, including subgroups and use of concomitant antithrombotic therapy, will be performed.

Bleeding events will be analysed according to adjudicated PLATO bleeding, the Thrombolysis in Myocardial Infarction (TIMI) Study Group and Bleeding Academic Research Consortium (BARC) class 3, 4, and 5 definitions (see the CEC charter).

MedDRA will be used for the coding and classification of AEs and SAEs in the database. AEs will be summarised by system organ class and preferred term using MedDRA. Summaries will be presented by treatment group using descriptive statistics. All AEs relating to bleeding will be summarised separately and the total number of bleeding events will be assessed.

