1.4 Benefit/risk and ethical assessment

Patients who experience ischaemic stroke or TIA are at high risk for developing subsequent events even when treated with aspirin, the current standard of care. Thrombosis risk is highest soon after the initial event, but treatment options are limited.

Ticagrelor requires no metabolic activation, providing a rapid onset and more consistent interpatient antiplatelet effect. In PLATO, in patients with ACS, on a background of aspirin, ticagrelor was superior to clopidogrel in reducing the rate of the composite efficacy endpoint of CV death, MI, and stroke (RRR 16%, ARR 1.9%; HR 0.84 [95% CI 0.77, 0.92]; p=0.0003) for up to 12 months of treatment.

Bleeding is the most important risk for all antiplatelet agents and especially dual antiplatelet therapy. Despite greater inhibition of platelet aggregation (IPA) with ticagrelor, results from the PLATO study showed that major bleeding with ticagrelor did not differ from that with clopidogrel on a background of aspirin. Although the total major bleeding did not differ between ticagrelor and clopidogrel in the PLATO study, non-procedural total major bleeding rates were significantly greater with ticagrelor compared to clopidogrel (3.1% vs 2.3%, HR 1.31 [95% CI 1.08, 1.60]; p = 0.006). In the CHANCE trial, clopidogrel plus aspirin was safe and effective compared to aspirin alone but the event rate on combination treatment was still very high with an 8.2% stroke risk at 90 days. These data confirm the need to further reduce the risk of recurrent stroke. Ticagrelor may be expected to reduce thrombotic events more effectively than currently approved therapies. Haemorrhagic risk is mitigated by excluding patients with large strokes and those with intracerebral haemorrhage. Adverse events (AE) observed in patients treated with ticagrelor, other than bleeding, include dyspnoea, and ventricular pauses that were largely asymptomatic. None of these events is considered to pose a significant risk as they can be adequately managed in the clinical setting.

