5.8.2 Permanent discontinuation from study medication

- Patient decision. The patient is at any time free to discontinue treatment, without prejudice to further treatment
- Investigator's decision, including but not limited to these examples:
 - 1. Incorrectly enrolled patient in whom the inclusion/exclusion criteria violation would put the patient at undue risk
 - 2. Adverse response thought to be related to the study medication for which the investigator thinks continued treatment may put the patient at undue risk
 - 3. Adverse event for which the investigator thinks continued treatment may put the patient at undue risk
 - 4. Severe non-compliance to study protocol
 - 5. Pregnancy
 - 6. Atrial fibrillation for which the patient receives anticoagulation therapy

Discontinuation of study medication does not mean discontinuation of follow-up or termination of study participation. Study assessments or telephone follow-up should be continued in all cases if possible, see Sections 5.8.3 and 5.9.

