12.1.2 Safety analysis set

All patients who received at least 1 dose of randomised ticagrelor or ASA, and for whom any post-dose data are available will be included in the safety population. Throughout the safety results sections, erroneously treated patients (eg, those randomised to ticagrelor but actually

given ASA) will be accounted for in the actual treatment group. Patients will be censored at 7 days after their last dose of study medication.

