12.2.4 Censoring

Patients who have not had the event(s) in question will be censored at the earliest of EoT Visit 5 (90 days) and the last study contact when all components of the endpoint in question were assessed. In the analysis of CV death and composites including CV death, censoring will occur at the date of death from non-cardiovascular causes. For endpoints not including death, all deaths are censoring events.

Complete endpoint information will be pursued with every effort for all patients regardless of their study medication status, unless they exercise their right to withdraw consent. Patients who have a non-fatal event will continue study follow-up. For patients who withdraw consent and for whom only vital status (known to be alive at study closure, or date of death) may be obtained from public records, the occurrence of all components of the primary endpoint cannot be assessed. Thus the primary endpoint and its components stroke, MI, and death will be censored at the time of consent withdrawal for those patients who withdraw consent and for whom only vital status is known from public records. However, the determination of all-cause death as a sole outcome event will utilise all publicly known mortality data, even that extending beyond date of consent withdrawal. The vital status information will be included in the analysis of all-cause death as a single secondary endpoint, in sensitivity analyses and tabulations.

Similarly, complete information on the primary endpoint may not be obtained for patients who are lost to follow-up (LTFU). Any such patient will be censored in the analysis of the primary composite endpoint at the last contact where all elements of the endpoint were assessed. A

patient will not be recorded as LTFU until the end of the study, after every allowable effort to get in contact has been made. Hence, it is anticipated that the number of patients LTFU will be limited.

Should it be that information about vital status after the End of Treatment Visit is collected for patients that are lost to follow-up, one sensitivity analysis will censor such observations at the date of the End of Treatment Visit and another will include all known events.

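### Kaplan-Meier with other-reason stoppers censored slightly overstates the proportion of patients who stop study drug because of bleeding; Aalen-Johansen should be used for this one endpoint

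*Protocol*

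**What the plan says.** Protocol section 12.2.2 lists two safety variables for time-to-event analysis from first dose: first PLATO major bleeding event, and "Discontinuation of study medication due to any bleeding event". Sections 2.3 and 12.2.2 both carry the second. For both variables, "Treatment groups will be compared using the Cox proportional hazards model with a factor for treatment group", and "Kaplan-Meier estimates of the cumulative incidence of each event will be calculated and plotted". No other estimator of cumulative incidence is named.

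Section 12.2.2 has no censoring rule of its own. The rule for the safety population is in section 12.1.2: "Patients will be censored at 7 days after their last dose of study medication". Section 12.2.4 adds: "For endpoints not including death, all deaths are censoring events".

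Section 5.8.2 lists reasons for permanent discontinuation that need not involve bleeding. They include the patient's own decision, other adverse events, severe non-compliance, pregnancy and "Atrial fibrillation for which the patient receives anticoagulation therapy". Sections 5.8.3 and 5.9 require the reason for stopping to be recorded in the eCRF.

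**The concern.** Stopping for bleeding and stopping for any other reason exclude each other: once a patient has permanently stopped, the other event cannot happen. Kaplan-Meier treats a censored patient as someone who could still have the event at the same rate as those still under observation. That is untrue for a patient who has left study drug for good. One-minus-Kaplan-Meier then estimates the risk in a setting where nobody ever stops for another reason. A reader who sees a curve labelled cumulative incidence will take it as the share of treated patients who stopped because of bleeding, and that share is lower.

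At stake is the accuracy of a displayed risk for a safety variable that section 2.3 singles out for specific focus. No confirmatory test is involved.

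**Working it through.** The protocol states no figure for this endpoint, so there is none to reproduce. The check compares the true proportion with what Kaplan-Meier would converge to under the stated censoring.

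**Inputs from the protocol.** Treatment lasts 90 days (section 5.5.2). Censoring is at last dose plus 7 days (section 12.1.2). About 13600 patients are randomised 1:1 (section 3.1), so about 6800 per arm.

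**Assumptions.** True proportion stopping for bleeding by Day 90, b = 1.5%. Proportion stopping for another reason (death included), o = 5% to 25%. Both cause-specific hazards constant.

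**Formulas.**
- Total hazard per day: λ = −ln(1 − b − o)/90.
- Bleeding-stop hazard: λ_b = λ·b/(b + o).
- Still on drug: S(t) = exp(−λt).
- Kaplan-Meier risk set, which keeps other-reason stoppers for 7 days: R(t) = S(t) + [o/(b + o)]·[S(max(t − 7, 0)) − S(t)].
- Kaplan-Meier limit: 1 − exp(−∫ λ_b·S(t)/R(t) dt), over 0 to 90 days.

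**Worked case, o = 20%.**
- λ = −ln(0.785)/90 = 0.24207/90 = 0.0026897.
- λ_b = 0.0026897 × 0.015/0.215 = 0.00018765.
- After Day 7, R/S = 1 + 0.9302 × (e^(7 × 0.0026897) − 1) = 1.01768.
- The integral is 0.001302 (Days 0 to 7) + 0.00018765 × 83/1.01768 = 0.001302 + 0.015305 = 0.016607.
- 1 − exp(−0.016607) = 1.647%, against a true 1.5%: +0.147 points, or +9.8%.

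**Range.**

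| Other-reason stops by Day 90 | One-minus-Kaplan-Meier (true 1.5%) | Absolute excess, points | Relative excess |
|---|---|---|---|
| 5% | 1.533% | 0.03 | 2.2% |
| 10% | 1.568% | 0.07 | 4.6% |
| 15% | 1.606% | 0.11 | 7.1% |
| 20% | 1.647% | 0.15 | 9.8% |
| 25% | 1.691% | 0.19 | 12.7% |

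An Aalen-Johansen estimate targets 1.5% in every row.

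**Sensitivity.**
- The relative excess hardly depends on b: for o of 5/10/15/20% it is 2.2/4.6/7.1/9.8% at b = 1% or 2%.
- With hazards concentrated early (exponential decay, 20-day constant) it falls to about 1.8/3.7/5.8/8.0%.
- Censoring at the moment of stopping would give 2.6/5.4/8.4/11.6/15.2% for o of 5/10/15/20/25%. The 7-day rule reduces the bias but does not remove it.

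**Scale.** The standard error of a 1.5% proportion in 6800 patients is √(0.015 × 0.985/6800) = 0.147 points. The excess is under half a standard error for o up to 10%, and about one standard error at o = 20%.

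**The case against.** **The general censoring rule may apply instead.** Section 12.2.4 censors patients without the event at the earlier of Visit 5 and the last contact at which the endpoint was assessed, and it follows patients whatever their medication status. Under that rule alone, other-reason stoppers would stay in the risk set to Day 90 and the bias from them would vanish. But section 12.1.2 is the rule specific to the safety set and ties censoring to the last dose. If the general rule was meant for this endpoint, the protocol does not say so.

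**The planned comparison is sound.** This stands. The arms are compared by a Cox hazard ratio, which under this censoring is a valid cause-specific hazard ratio. Kaplan-Meier estimates are only calculated and plotted, and no Kaplan-Meier risk difference is planned.

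**The arms may be affected unequally.** A reader might infer a distorted treatment contrast, because section 1.4 says that ticagrelor's adverse effects "other than bleeding, include dyspnoea, and ventricular pauses that were largely asymptomatic". The documents do not support that step. They give no stopping rate for either arm, and the same paragraph says these effects can be managed. If other-reason stopping were 20% in one arm and 10% in the other, equal true proportions of 2% would be displayed as 2.20% and 2.09%; that split is an assumption.

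**It is small and descriptive.** Also true. It limits the weight of the point without making the stated estimator right.

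**Conclusion.** The point holds for one endpoint and one estimator. As written, one-minus-Kaplan-Meier overstates the proportion of patients who stop study medication because of bleeding. At an assumed true 1.5%, with constant hazards and the 7-day rule, the overstatement is about 2.2% to 12.7% in relative terms (0.03 to 0.19 points) for other-reason stops of 5% to 25%. The direction follows from the method; the size rests on assumed stopping rates. A between-arm bias would arise only if other-reason stopping differed by arm, which the documents do not establish.

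A reader might also carry the criticism to MI, ischaemic stroke and CV death, where deaths are censored too. There, follow-up continues after study drug is stopped, so only death competes. Death is one component of a composite whose blinded rate is about 6.4% (section 12.3), so the effect would be negligible, and no change is asked for.

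This is a minor improvement, with no bearing on the primary analysis, alpha or sample size.

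**What to change.** Add to section 12.2.2, for this endpoint only: *Cumulative incidence of discontinuation due to bleeding will be estimated by the Aalen-Johansen method, with permanent discontinuation for any other reason and death as competing events; the Cox hazard ratio is reported as cause-specific.*

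The cost is one sentence and a different estimator in the programming. The reason for stopping is already collected, and the Cox model stays as planned.

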12.2.3 Interim analyses

One interim analysis will be performed by the DMC following the accrual and confirmation by adjudication of 50% of planned primary events (422). The study may be stopped either for futility or for efficacy. The efficacy stopping boundary at the interim analysis is a 2-sided p-value <0.001 for the primary endpoint (composite of stroke, MI, and death). The interim p-value is small enough for the final analysis to be conducted at a significance level of 4.98%, with the family wise error rate controlled at 5.00%. These boundaries were estimated in East V5.2 using a Haybittle-Peto procedure (Haybittle 1971, Peto 1976). The futility stopping boundary is to stop if the observed HR for the primary endpoint is >0.954, corresponding to a predictive power of 10%. This provides > 88.7% overall power at the end of the study.

If a recommendation to stop the study for efficacy is made at the interim, all subsequent testing will be done at the same significance level as for the interim.

The DMC charter contains more information about the DMC procedures. A copy of the treatment codes will be made available to the statistician on the DMC. The Executive Committee and AstraZeneca will not be made aware of the treatment codes until after clean file and database lock are declared. Similarly, all summary output reviewed at each DMC meeting will be held in confidence by the DMC members until the end of the study when clean file and database lock are declared. Further details are given in the DMC charter.

12.2.4 Censoring

Patients who have not had the event(s) in question will be censored at the earliest of EoT Visit 5 (90 days) and the last study contact when all components of the endpoint in question were assessed. In the analysis of CV death and composites including CV death, censoring will occur at the date of death from non-cardiovascular causes. For endpoints not including death, all deaths are censoring events.

Complete endpoint information will be pursued with every effort for all patients regardless of their study medication status, unless they exercise their right to withdraw consent. Patients who have a non-fatal event will continue study follow-up. For patients who withdraw consent and for whom only vital status (known to be alive at study closure, or date of death) may be obtained from public records, the occurrence of all components of the primary endpoint cannot be assessed. Thus the primary endpoint and its components stroke, MI, and death will be censored at the time of consent withdrawal for those patients who withdraw consent and for whom only vital status is known from public records. However, the determination of all-cause death as a sole outcome event will utilise all publicly known mortality data, even that extending beyond date of consent withdrawal. The vital status information will be included in the analysis of all-cause death as a single secondary endpoint, in sensitivity analyses and tabulations.

Similarly, complete information on the primary endpoint may not be obtained for patients who are lost to follow-up (LTFU). Any such patient will be censored in the analysis of the primary composite endpoint at the last contact where all elements of the endpoint were assessed. A

patient will not be recorded as LTFU until the end of the study, after every allowable effort to get in contact has been made. Hence, it is anticipated that the number of patients LTFU will be limited.

Should it be that information about vital status after the End of Treatment Visit is collected for patients that are lost to follow-up, one sensitivity analysis will censor such observations at the date of the End of Treatment Visit and another will include all known events.

12.2.5 Post study follow-up period

Data collected at Study Closure Visit will be presented using descriptive statistics per treatment. The FAS will be used for the efficacy endpoints and the safety analysis set will be used for the adverse events.

12.3 Determination of sample size

Based on data from the FASTER trial (Kennedy 2007), CHANCE trial (Wang 2013) and SCAST trial (Sandset 2011) a primary endpoint (stroke, MI, death) rate of 10% in the ASA arm is assumed at 3 months following randomisation. A HR in favour of ticagrelor of 0.8, is also assumed. Blind data review has revealed a lower than anticipated primary endpoint rate of approximately 6.4% instead of the 9% originally anticipated. Randomising 13600 patients to the ASA and ticagrelor in a 1:1 ratio is expected to yield the 844 primary events providing 88.7% power at the final significance level of 4.98%, defined in Section 12.2.3. The study is event driven and the number of patients is estimated to ensure collection of 844 events. The final number of randomised patients will depend on the collection of the primary events and the actual sample size will be determined based on blind data review.

12.4 Data monitoring committee

See Section 5.10.

13.2 Overdose

An overdose of ticagrelor is defined as an intake of greater than 4 ticagrelor tablets/day during the maintenance phase.

In the event of an overdose with ticagrelor, the investigator must ascertain the time and extent of the overdose regardless of severity. The investigator should determine the causative circumstance and whether haemorrhagic or toxic complications have occurred or are likely to do so. Depending on these facts it must be decided whether the patient should be hospitalized for observation or not. Bleeding is one of the most likely pharmacological effects of excessive ticagrelor dosing, and appropriate supportive measures such as volume replacement, local haemostatic measures, and decompression or drainage may be required depending on the extent of bleeding or volume of blood lost. Patients with overdose-related bleeding should be cautioned to avoid unnecessary activity, mechanical tissue stress, and minor trauma for at least 24 hours after the bleeding has stopped. For other symptoms that can be expected after an overdose of ticagrelor and additional information see the IB.

- An overdose with associated AEs is recorded as the AE diagnosis/symptoms on the relevant AE modules in the eCRF and on the Overdose eCRF module.
- An overdose without associated symptoms is only reported on the Overdose eCRF module.

If an overdose on an AstraZeneca study drug occurs in the course of the study, then investigators or other site personnel inform appropriate AstraZeneca representatives immediately, or **no later than 24 hours** of when he or she becomes aware of it.

The designated AstraZeneca representative works with the investigator to ensure that all relevant information is provided to the AstraZeneca Patient Safety data entry site.

For overdoses associated with SAE, standard reporting timelines apply, see Section 6.4.4. For other overdoses, reporting should be done within 30 days.

13.3 Pregnancy

All outcomes of pregnancy should be reported to AstraZeneca.

13.3.1 Maternal exposure

If a patient becomes pregnant during the course of the study, the study medication should be discontinued immediately.

Pregnancy itself is not regarded as an adverse event unless there is a suspicion that the study medication under study may have interfered with the effectiveness of a contraceptive medication. Congenital abnormalities/birth defects and spontaneous miscarriages should be reported and handled as SAEs. Elective abortions without complications should not be handled as AEs. The outcome of all pregnancies (spontaneous miscarriage, elective termination, ectopic pregnancy, normal birth or congenital abnormality) should be followed up and documented even if the patient was discontinued from the study.

If a pregnancy on an AstraZeneca study medication occurs during the course of the study, then investigators or other site personnel should inform appropriate AstraZeneca representatives immediately, or **no later than 24 hours** of when he or she becomes aware of it.

The designated AstraZeneca representative works with the investigator to ensure that all relevant information is provided to the AstraZeneca Patient Safety data entry site within 1 or 5 days for SAEs, see Section 6.4.4, and within 30 days for all other pregnancies.

The same timelines apply when outcome information is available.

The PREGREP module in the eCRF is used to report the pregnancy and the PREGOUT is used to report the outcome of the pregnancy.

13.3.2 Paternal exposure

There are no restrictions against fathering a child when treated with ticagrelor. If paternal exposure pregnancy occurs in the course of the study, then investigators or other site personnel should inform appropriate AstraZeneca representatives immediately, or no later than **24 hours** as described in the maternal exposure Section 13.3.1.

Appendix B Additional Safety Information

FURTHER GUIDANCE ON THE DEFINITION OF A SERIOUS ADVERSE EVENT (SAE)

Life threatening

'Life-threatening' means that the subject was at immediate risk of death from the AE as it occurred or it is suspected that use or continued use of the product would result in the subject's death. 'Life-threatening' does not mean that had an AE occurred in a more severe form it might have caused death (eg, hepatitis that resolved without hepatic failure).

Hospitalisation

Outpatient treatment in an emergency room is not in itself a serious AE, although the reasons for it may be (eg, bronchospasm, laryngeal oedema). Hospital admissions and/or surgical operations planned before or during a study are not considered AEs if the illness or disease existed before the subject was enrolled in the study, provided that it did not deteriorate in an unexpected way during the study.

Important medical event or medical intervention

Medical and scientific judgement should be exercised in deciding whether a case is serious in situations where important medical events may not be immediately life threatening or result in death, hospitalisation, disability or incapacity but may jeopardize the subject or may require medical intervention to prevent one or more outcomes listed in the definition of serious. These should usually be considered as serious.

Simply stopping the suspect drug does not mean that it is an important medical event; medical judgement must be used.

Examples of such events are:

- Angioedema not severe enough to require intubation but requiring iv hydrocortisone treatment
- Hepatotoxicity caused by paracetamol (acetaminophen) overdose requiring treatment with N-acetylcysteine
- Intensive treatment in an emergency room or at home for allergic bronchospasm
- Blood dyscrasias (eg, neutropenia or anaemia requiring blood transfusion, etc) or convulsions that do not result in hospitalisation
- Development of drug dependency or drug abuse.

A GUIDE TO INTERPRETING THE CAUSALITY QUESTION

The following factors should be considered when deciding if there is a "reasonable possibility" that an AE may have been caused by the drug.

- Time Course. Exposure to suspect drug. Has the subject actually received the suspect drug? Did the AE occur in a reasonable temporal relationship to the administration of the suspect drug?
- Consistency with known drug profile. Was the AE consistent with the previous knowledge of the suspect drug (pharmacology and toxicology) or drugs of the same pharmacological class? OR could the AE be anticipated from its pharmacological properties?
- Dechallenge experience. Did the AE resolve or improve on stopping or reducing the dose of the suspect drug?
- No alternative cause. The AE cannot be reasonably explained by another aetiology such as the underlying disease, other drugs, other host or environmental factors.
- Rechallenge experience. Did the AE reoccur if the suspected drug was reintroduced after having been stopped? AstraZeneca would not normally recommend or support a rechallenge.
- Laboratory tests. A specific laboratory investigation (if performed) has confirmed the relationship?

A "reasonable possibility" could be considered to exist for an AE where one or more of these factors exist.

In contrast, there would not be a "reasonable possibility" of causality if none of the above criteria apply or where there is evidence of exposure and a reasonable time course but any dechallenge (if performed) is negative or ambiguous or there is another more likely cause of the AE.

In difficult cases, other factors could be considered such as:

- Is this a recognised feature of overdose of the drug?
- Is there a known mechanism?

Ambiguous cases should be considered as being a "reasonable possibility" of a causal relationship unless further evidence becomes available to refute this. Causal relationship in cases where the disease under study has deteriorated due to lack of effect should be classified as no reasonable possibility.

Clinical Study Protocol Appendix C

Drug Substance Ticagrelor

Study Code D5134C00001

Edition Number 2

Date 5 June 2014

